
Secondary for Part A
 
 To evaluate the efficacy of baricitinib in children with JIA-U or ANA-positive uveitis in the most severely affected eye and less affected eye To evaluate the efficacy of adalimumab in children with JIA-U or ANA-positive uveitis in the most severely affected eye and less affected eye 	
 Change in SUN grade of cells in the anterior chamber through Week 24 in the most severely affected eye. Change in SUN grade of cells in the anterior chamber through Week 24 in the less severely affected eye (if applicable). In patients with bilateral uveitis disease at baseline: Proportion of responders at Week 24, defined according to the SUN criteria as a 2-step decrease in the level of anterior chamber cells in the most severely affected eye at baseline (or both eyes if the inflammation grade is the same in both eyes) and a 1-step decrease in the level of anterior chamber cells in the less severely affected eye at baseline^a. Change in visual acuity measured by age-appropriate LogMAR test through Week 24. Change in vitreous haze through Week 24 in each affected eye. Change in grade of flare in the anterior chamber through Week 24 in each affected eye. Change in overall uveitis-related disability: 
 Change in Patient Uveitis-related Disease Activity through Week 24. Change in Patient Uveitis-related Improvement at Week 12 and Week 24. Change in Patient Arthritis Disease Activity through Week 24. Change in Patient Arthritis Improvement at Week 12 and Week 24. Change in Ophthalmologist Uveitis-related Disease Activity through Week 24.

Objectives	Endpoints
	
 ○ Change in Ophthalmologist Uveitis-related Improvement at Week 12 and Week 24. ● Proportion of patients with inactive anterior uveitis (using SUN definition) in each affected eye through Week 24. ● Time to inactive anterior uveitis disease (using SUN definition) in each affected eye. ● Proportion of patients who are able to taper concomitant topical corticosteroids to <2 drops per day and to 0 drops per day. ● PediACR30/50/70/90/100 response rates (for patients with JIA-U).

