Overall means for the individual CHQ scales and items will be scored according to the scoring manual. Scores will be transformed to ensure that all items are positively scored so that a higher score indicates better health (HealthActCHQ 2013). In addition, 2 summary scores, the Physical Summary Score (PhS) and Psychosocial Summary Score (PsS), will be evaluated based upon 10 scales of the CHQ-PF50. United States norms are available for the CHQ-PF50. The response options for the CHQ-PF50 vary from 4 to 6 levels for the scales. The majority of the items have a recall period of 4 weeks. Data will be captured on an electronic tablet.

Morning Joint Stiffness Duration

As one of the assessments to determine inactive disease, the physician will ask the parent/legal guardian if the duration of their child's morning joint stiffness was >15 minutes since the previous visit; inactive disease is ≤ 15 minutes in duration. Responses are yes/no.

Patient Uveitis-related Disease Activity

The Patient Uveitis-related Disease Activity instrument is a single-item question. It is completed by caregivers/legal guardians (proxy) for children less than 8 years; for children aged 8 years or older, this will be self-completed. The single item asks the respondent to rate their eye problems "at this time". It uses a 4-item Likert scale (1 = "None", 2 = "Mild", 3 = "Moderate", and 4 = "Severe").

Patient Uveitis-related Improvement

The Patient Uveitis-related Improvement instrument is a single-item question. It is completed by caregivers/legal guardians (proxy) for children less than 8 years; for children aged 8 years or older, this will be self-completed. The item asks the respondent to rate the overall change in their eye problems since they started taking study medication. It uses a 5-item Likert scale (1 = "Much Better", 2 = "A little Better", 3 = "No Change", 4 = "A Little Worse", and 5 = "Much Worse").

Patient Arthritis Disease Activity

The Patient Arthritis Disease Activity instrument is a single-item question. It is completed by caregivers/legal guardians (proxy) for children less than 8 years; for children aged 8 years or older, this will be self-completed. The item asks the respondent to rate their arthritis "at this time". It uses a 4-item Likert scale (1 = "None", 2 = "Mild", 3 = "Moderate", and 4 = "Severe").

Patient Arthritis Improvement

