10.3.3.2. Secondary Analyses

Secondary efficacy and health outcomes analyses (Table JAHW.12) will be based on all participants who take at least 1 age-based dose of investigational product for Part A. Baseline is defined as Week 0.

The secondary efficacy and health outcomes analysis for Part B will be addressed in the SAP.

Table JAHW.12. Secondary Efficacy Endpoint Analyses for Part A

Measure	Endpoint	Analysis Method
SUN grade of cells in the anterior chamber in the most severely affected eye	Change from baseline	Summary statistics
SUN grade of cells in the anterior chamber in the less severely affected eye (if applicable)	Change from baseline	Summary statistics
In patients with bilateral uveitis disease at baseline: Responders, defined according to the SUN criteria as a 2-step decrease in the level of anterior chamber cells in the most severely affected eye at baseline (or both eyes if the inflammation grade is the same in both eyes) and a 1-step decrease in the level of anterior chamber cells in the less severely affected eye at baseline.	Proportion of patients	Summary statistics
Visual acuity by age-appropriate LogMAR test in each eye	Change from baseline	Summary statistics
Vitreous haze in each affected eye	Change from baseline	Summary statistics
Grade of flare in the anterior chamber in each affected eye	Change from baseline	Summary statistics
Overall uveitis-related disability: 
 ○ Change in Patient Uveitis-related Disease Activity through Week 24. ○ Change in Patient Uveitis-related Improvement at Week 12 and Week 24. ○ Change in Patient Arthritis Disease Activity through Week 24. ○ Change in Patient Arthritis Improvement at Week 12 and Week 24. ○ Change in Ophthalmologist Uveitis-related Disease Activity through Week 24. ○ Change in Ophthalmologist Uveitis-related Improvement at Week 12 and Week 24. 	Change from baseline	Shift table
Proportion of patients with inactive anterior uveitis disease status in each affected eye	Proportion of affected eyes	Summary statistics
	Time to inactive disease status	Summary statistics

Measure	Endpoint	Analysis Method
Concomitant topical corticosteroid tapering status, for patients eligible for corticosteroid tapering	Proportion of patients	Summary statistics
PediACR 30/50/70/90/100	Proportion of responders	Summary statistics

Abbreviations: PediACR = Pediatric American College of Rheumatology; SUN = Standardization of Uveitis Nomenclature.

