Patient Uveitis-related Disease Activity	The Patient Uveitis-related Disease Activity instrument is a single-item question. It is completed by caregivers/legal guardians (proxy) for children less than 8 years; for children aged 8 years or older, this will be self-completed. The single item asks the respondent to rate their eye problems “at this time”. It uses a 4-item Likert scale (1 = “None”, 2 = “Mild”, 3 = “Moderate”, and 4 = “Severe”).	▪ Patient Uveitis-related Disease Activity.	Change from baseline: observed Patient Uveitis-related Disease Activity – baseline Patient Uveitis-related Disease Activity	Missing if baseline or observed value is missing.
Patient Uveitis-related Improvement	The Patient Uveitis-related Improvement instrument is a single-item question. It is completed by caregivers/legal guardians (proxy) for children less than 8 years; for children aged 8 years or older, this will be self-completed. The item asks the respondent to rate the overall change in their eye problems since they started taking study medication. It uses a 5-item Likert scale (1 = “Much Better”, 2 = “A little Better”, 3 = “No Change”, 4 = “A Little Worse”, and 5 = “Much Worse”).	▪ Patient Uveitis-related Improvement	Patient uveitis related improvement score at analysis visit	Missing if baseline or observed value is missing.

Measure	Description	Variable	Derivation / Comment	Definition of Missing
Patient Arthritis Disease Activity	The Patient Arthritis Disease Activity instrument is a single-item question. It is completed by caregivers/legal guardians (proxy) for children less than 8 years; for children aged 8 years or older, this will be self-completed. The item asks the respondent to rate their arthritis “at this time”. It uses a 4-item Likert scale (1 = “None”, 2 = “Mild”, 3 = “Moderate”, and 4 = “Severe”).	▪ Patient Arthritis Disease Activity score	Change from baseline: observed Patient Arthritis Disease Activity – baseline Patient Arthritis Disease Activity	Missing if baseline or observed value is missing.

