Patient Arthritis Improvement	The Patient Arthritis Improvement instrument is a single-item question. It is completed by caregivers/legal guardians (proxy) for children less than 8 years; for children aged 8 years or older, this will be self-completed. The question asks the respondent to rate the overall change in their arthritis since they started taking study medication. It uses a 5-item Likert scale (1 = “Much Better”, 2 = “A little Better”, 3 = “No Change”, 4 = “A Little Worse”, and 5 = “Much Worse”).	▪ Patient Arthritis Improvement score	Patient Arthritis Improvement score at analysis visit	Missing if baseline or observed value is missing.

Measure	Description	Variable	Derivation / Comment	Definition of Missing
Ophthalmologist Uveitis-related Disease Activity	The Ophthalmologist Uveitis-related Disease Activity instrument is a single-item question asking the ophthalmologist to rate their patients' disease activity in each eye "at this time". It uses a 4-item Likert scale (1 = "None", 2 = "Mild", 3 = "Moderate", and 4 = "Severe").	▪ Ophthalmologist Uveitis-related Disease Activity score	Change from baseline: observed Ophthalmologist Uveitis-related Disease Activity – baseline Ophthalmologist Uveitis-related Disease Activity	Missing if baseline or observed value is missing.
Ophthalmologist Uveitis-related Improvement	The Ophthalmologist Uveitis-related Improvement instrument is a single-item question asking the ophthalmologist to rate the overall change in their patients' uveitis in each eye since they started taking study medication. It uses a 5-item Likert scale (1 = "Much Better", 2 = "A little Better", 3 = "No Change", 4 = "A Little Worse", and 5 = "Much Worse").	▪ Ophthalmologist Uveitis-related Improvement score	Change from baseline: observed Ophthalmologist Uveitis-related Improvement – baseline Ophthalmologist Uveitis-related Improvement	Missing if baseline or observed value is missing.

Table JAHW.7.4. Secondary Efficacy Endpoint Analyses for Part A

Measure	Endpoint	Analysis Method	Handling of Missing Data
Patient Uveitis-related Disease Activity	Change from baseline	Summary statistics	LOCF
Patient Uveitis-related Improvement	Change from baseline	Summary statistics	LOCF
Patient Arthritis Disease Activity	Change from baseline	Summary statistics	LOCF
Patient Arthritis Improvement	Change from baseline	Summary statistics	LOCF
Ophthalmologist Uveitis-related Disease Activity	Change from baseline	Summary statistics	LOCF

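### Three Improvement scales that rate change since starting study drug are analysed as change from a baseline that is never collected, so the SAP's missing-value rule leaves no computable values

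*SAP*

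**What the plan says.** Protocol Section 9.1.3 and SAP Table JAHW.7.3 describe three single-item Improvement instruments, each scored from 1 (Much Better) to 5 (Much Worse). In the SAP's words:

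- Patient uveitis: "The item asks the respondent to rate the overall change in their eye problems since they started taking study medication".
- Patient arthritis: "The question asks the respondent to rate the overall change in their arthritis since they started taking study medication".
- Ophthalmologist uveitis: a single question "asking the ophthalmologist to rate the overall change in their patients' uveitis in each eye since they started taking study medication".

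The endpoint lists (protocol Table JAHW.5, SAP Table JAHW.4.2) name two time points for each, for example "Change in Patient Uveitis-related Improvement at Week 12 and Week 24". Three companion Disease Activity scales rate current state and are followed through Week 24.

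The analysis instructions are:

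- **SAP Table JAHW.7.3, derivation column.** Ophthalmologist scale: "Change from baseline: observed Ophthalmologist Uveitis-related Improvement – baseline Ophthalmologist Uveitis-related Improvement". The two patient scales: the score at the visit being analysed, with no subtraction.
- **SAP Table JAHW.7.3, missing column.** The same entry for all three: "Missing if baseline or observed value is missing".
- **SAP Table JAHW.7.4.** A separate row for each scale, all with change from baseline as the endpoint, summary statistics as the method and LOCF for missing data.
- **SAP Table JAHW.7.2.** One row for all six disability items: change from baseline, summary statistics, LOCF.
- **Protocol Table JAHW.12.** One row for the same six items, including "Change in Ophthalmologist Uveitis-related Improvement at Week 12 and Week 24": change from baseline, shown in a shift table.

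**The concern.** An Improvement item is already a statement of change. It has no value before treatment starts, so subtracting a baseline from it is undefined, and requiring a baseline before a score counts as present excludes every patient. The SAP also contradicts itself on the two patient scales: the derivation column uses the visit score, while the missing rule beside it and Table JAHW.7.4 both need a baseline.

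At stake are three of the six disability items in both arms. Whoever programs the tables would have to choose between an empty table, the raw score, and a difference from an assumed baseline of No Change. Protocol Section 9.1.6 describes these scales as new instruments developed by the sponsor, and neither document cites a scoring manual for them, so the SAP is where the choice has to be settled. The trial is open-label, and it is better settled before the tables are programmed.

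**Working it through.** There is no power or sample-size figure to reproduce. The check applies the SAP's rules to the visit schedule.

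**Step 1. Can a baseline exist?** SAP Section 6.1.2 defines baseline as the visit of the first dose, and SAP Section 7.2 gives it as Week 0. Protocol Section 5.1.1 has all baseline assessments completed before the first dose. The items ask about change since study medication started, so they cannot be answered at that point.

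**Step 2. Is one collected?** In protocol Table JAHW.1:

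| Scales | Screening (V1) | Baseline (V2) | Treatment period after baseline | ETV and V801 |
|---|---|---|---|---|
| Three Disease Activity scales | yes | yes | every visit | yes |
| Three Improvement scales | no | no | two visits | yes |

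In text extracted from the PDF, the two treatment-period marks for the Improvement scales appear one column to the left of Week 12 and Week 24. The CHQ-PF50 row shows the same displacement and still has its V2 mark, so the displacement does not explain the absence of a baseline mark for the Improvement scales.

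**Step 3. Apply the missing rule.** Under Table JAHW.7.3 a value is present only if the baseline value and the observed value are both present. Scheduled baseline values: 0.

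- Planned minimum number of patients (protocol Section 5.2): 20 + 4 = 24.
- Computable values per scale at Week 12: 0 of 24.
- Computable values per scale at Week 24: 0 of 24.
- Scales affected: 3 of the 6 listed disability items.

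**Step 4. Does imputation help?** SAP Section 6.3.2 carries forward the last nonmissing postbaseline observation. That can fill a later visit but cannot create a baseline, and there is no nonmissing derived value to carry.

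**Step 5. Would an assumed baseline help?** Suppose every patient were given 3 (No Change) at baseline. The derived value would be the score minus 3, which runs from 1 − 3 = −2 to 5 − 3 = +2. Subtracting a constant leaves the spread and the category counts as they were, so no information is lost, but a rating of change would be labelled as a change in that rating. Neither document provides for this.

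**Step 6. Remove the baseline condition.** If a value is missing only when the observed score is missing, up to 24 of 24 patients can be analysed per scale at each of the two visits. The ophthalmologist scale is rated for each eye, so it can give more than one value per patient.

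**The case against.** The strongest reply is that two of the three scales are already derived correctly. Table JAHW.7.3 uses the visit score for both patient scales, and the missing entry beside it is the same sentence in all six rows of that table, which suggests template text carried over. On that reading only the ophthalmologist scale is defective, the scores are still collected, and a sensible programmer would report them. The evidence from SAP Table JAHW.7.2 and protocol Table JAHW.12 is also weaker than it first looks, because each has one shared row for six items. Finally, the consequence is small: the documents define no composite disability score, no treatment comparison is planned, there is no multiplicity control, and the primary Bayesian analysis does not use these scales.

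Much of this stands. The error may well be carry-over, the impact is confined to descriptive secondary endpoints, and for the patient scales the fault is a contradiction rather than a wrong formula. It does not rescue those two scales, however. The derivation and missing columns apply together, nothing says that the derivation prevails, and Table JAHW.7.4 lists each scale on its own row as change from baseline. For the ophthalmologist scale, the derivation, missing rule and Table JAHW.7.4 all agree on a quantity that cannot be computed.

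**Conclusion.** The concern holds. As written, the SAP gives no computable value on any of the three Improvement scales: 0 of 24 patients at the planned minimum, at Week 12 and at Week 24, for three of the six disability items. For the ophthalmologist scale the derivation itself is wrong. For the two patient scales the derivation is sound but is contradicted by the missing rule and by Table JAHW.7.4.

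This rests on reading the columns of Table JAHW.7.3 together and on no baseline value being collected, which the item wording, the endpoint time points and the schedule all support. The loss comes from the rule, since the Week 12 and Week 24 scores will be in the database. The tables should be corrected before programming, but the trial's main conclusion does not depend on it.

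**What to change.** 1. **SAP Table JAHW.7.3.** Derive the ophthalmologist scale as the score at the visit, as for the two patient scales. For all three, define a value as missing only when the observed score is missing.
2. **SAP Tables JAHW.7.2 and JAHW.7.4.** Replace change from baseline with the score at Week 12 and Week 24 for the three Improvement scales, splitting the shared row of Table JAHW.7.2. Counts and percentages in the five categories by arm, and by eye for the ophthalmologist scale, suit an ordinal item better than means. LOCF can stay, since it would then have a score to carry.
3. **Protocol Table JAHW.12.** Split the shared row in the same way. Keep change from baseline and the shift table for the three Disease Activity scales only. This also removes the mismatch between the protocol's shift table and the SAP's summary statistics for the Improvement scales.
4. **Optional.** Drop the words that label these endpoints as a change. This is a matter of wording and would also touch the protocol synopsis, protocol Table JAHW.5, protocol Section 9.1.2 and SAP Table JAHW.4.2.

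The cost is table wording, with no new data and no effect on the primary analysis. Protocol Section 10.3.1 requires an amendment only when a principal feature changes. If this change is judged not to be one, the protocol table can follow at the next amendment, with the change and its reason described in the clinical study report.

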7.2. Secondary Efficacy Analyses

Secondary efficacy analyses ([Table JAHW.7.1](#)) will be based on all participants who take at least 1 age-based dose of investigational product for Part A. Baseline is defined as Week 0.

The secondary efficacy and health outcomes analyses for Part B will be summarized in descriptive statistics.

7.3. Health Outcomes/Quality-of-Life Analyses

Health outcomes and quality-of-life related analyses for Part A are listed in [Section 4.2](#) and [Table JAHW.7.3](#).

7.4. Bioanalytical and Pharmacokinetic/Pharmacodynamic Methods

PK, pharmacodynamic (PD) and biomarker analyses to address secondary and exploratory objectives of this study will be described by Lilly in separate PK/PD and biomarker analysis plans.

7.5. Evaluation of Immunological Measures

Change from baseline in immunoglobulin levels and peripheral blood immunophenotyping (including T and B cells, T cell subsets, and NK cells) will be evaluated and summarized using descriptive statistics. Patients who are immunized with tetanus-diphtheria-acellular pertussis (TDaP) or pneumococcal conjugate vaccines will have their IgG antibody titers to the antigens evaluated preimmunization and at 4 and 12 weeks postimmunization. A primary immune response will be assessed in patients who have never received TDaP or pneumococcal conjugate vaccines previously, and secondary/booster responses will be assessed if the patients have previously received the vaccines.

8. Safety Analyses

The planned safety analyses are consistent with compound-level standards, which are based on various sources, including company standards, internal and external subject matter experts, and cross-industry initiatives (e.g., white papers produced by a PHUSE Computational Science Working Group [a collaboration with FDA and PHUSE], published in the PHUSE Deliverables Catalog). Descriptions of the safety analyses are provided in this SAP; however, some details are in compound-level safety standards.

For Study JAHW, the following treatment groups and summary for each study period and analysis population are described below in [Table JAHW.8.1](#).

Table JAHW.8.1. Summary of Safety Analysis Population, Baseline and Postbaseline

Population for safety analysis	Part A safety population		Long-term safety population	
	Bari	Ada	Bari	Ada
Treatment period	Part A		Part A+B	
Postbaseline definition	Start with first dose of study treatment, end until treatment period plus up to 30 days off-drug follow-up time	Start with first dose of study treatment, end until treatment period plus up to 30 days off-drug follow-up time.	First day of Bari administration up to data cut for ongoing patients or up to 30 days after the last dose of Bari as long as the patient is in the program.	First day of Ada administration up to data cut for ongoing patients or up to the first dose of Bari or end of study participation as long as the patient is in the program.
Baseline for LLT used in defining treatment-emergence	Screening period up to date of first dose of study treatment.			

Abbreviations: Ada = adalimumab; Bari = baricitinib; LLT = Lowest Level Term.

8.1. Extent of Exposure

Duration of exposure (in days) to study drug will be summarized for each treatment period with corresponding safety population, which is defined in [Table JAHW.8.1](#).

Total patient years (PY) of exposure will be reported for overall duration of exposure. Descriptive statistics (n, mean, SD, minimum, 1st quartile, median, 3rd quartile and maximum) will be provided for patient-days of exposure, and the frequency of patients falling into different

exposure ranges will be summarized. Exposure ranges will generally be reported in weeks using the following as a general guide:

For Part A safety analysis population (see [Table JAHW.8.1](#))

- ≥ 4 weeks, ≥ 8 weeks, ≥ 16 weeks, ≥ 24 weeks
- >0 to <4 weeks, ≥ 4 weeks to <8 weeks, ≥ 8 weeks to <16 weeks, ≥ 16 weeks to <24 weeks

For long-term safety analysis population (see [Table JAHW.8.1](#)):

- Every 24 weeks or semi-annually

Overall exposure will be summarized in total PY which is calculated according to the following formula:

$$PYE = \text{sum of duration of exposure in days (for all patients in treatment group)} / 365.25$$

